Appendix 5 Liver Safety: Suggested Actions and Follow-up Assessments

The Investigator will consider discontinuation of study intervention for abnormal liver function when a participant meets one of the conditions outlined in the algorithm or if the Investigator believes that it is in best interest of the participant.

All confirmed events of ALT or AST $\geq 5 \times$ ULN triggers stopping criteria.

All confirmed events of ALT or AST $\geq 3 \times$ ULN and total bilirubin $> 2 \times$ ULN triggers stopping criteria.

All AEs involving the liver or the gall bladder will be reported as AESI according to the risk profile of evobrutinib.

Appendix 6 Clinical Laboratory Tests

The protocol-required clinical laboratory assessments are in the following table:

Laboratory Assessment	Parameter	Notes
Biochemistry	Albumin	
	Alanine Aminotransferase	
	Alkaline Phosphatase	
	Amylase	
	Aspartate Aminotransferase	
	Bicarbonate	
	Total Bilirubin	
	Blood Urea Nitrogen	
	Calcium	
	Chloride	
	Cholesterol	
	Creatinine	
	Creatine Phosphatase	
	Glomerular Filtration Rate, Estimated	Refer to SoA
	Gamma Glutamyl Transferase	
	Glucose	
	Inorganic Phosphate	
	Lactate Dehydrogenase	
	Lipase	
	Magnesium	
	Potassium	
	Sodium	
	Triglycerides	
	Urate	
Coagulation	
 Prothrombin Intl. Normalized Ratio Activated partial thromboplastin time 	
Hematology	Hematocrit	
	Hemoglobin	
	Leukocytes with Differential:	
	Neutrophils (absolute/%)	
	Lymphocytes (absolute/%)	
	Monocytes (absolute/%)	
	Eosinophils (absolute/%)	
	Basophils (absolute/%)	
	Mean Corpuscular Hemoglobin (MCH)	
	Mean Corpuscular Volume (MCV)	
	Platelets	
	Erythrocytes	

Laboratory Assessment	Parameter	Notes
Hormonal	Thyroid stimulating Hormone	
Routine Urinalysis	Specific gravity, pH, glucose, protein, blood, ketones, bilirubin, urobilinogen, nitrite, leukocyte esterase by dipstick.	
	Microscopic examination (if blood or protein is abnormal with positive dipstick).	
	In case of a positive result for hemoglobin, leukocyte esterase, protein or nitrite, a flow cytometry count and classification will be performed.	
Pregnancy Testing	Serum human Choriongonadotropin Beta pregnancy test	At all timepoints listed in the SoA (see Section 1.3).
Other Screening Tests	
 • Follicle stimulating hormone • Urine drug screen (to include at minimum: amphetamine, methamphetamine, barbiturates, 3,4-methylenedioxymethamphetamine [ecstasy], cocaine, opiate, cannabinoids, benzodiazepine, methadone, phencyclidine, oxycodone, and tricyclic antidepressants.) • Serology (HIV-1/2 Antibody, hepatitis B virus surface antigen, hepatitis B virus core antibody, hepatitis C virus antibody, QuantiFERON test) • SARS-CoV-2 antigen • Thyrotropin (thyroid stimulating hormone) • Cotinine • Ethanol (Alcohol breath test) • Estimated Glomerular Filtration Rate based on Chronic Kidney Disease Epidemiology Collaboration Creatinine Equation (2009) 	
All study-required laboratory assessments will be performed by a central laboratory (Nuvisan's clinical laboratory)
 
At Screening and Day -1 of each period.
 
At Screening and Day -1 of each period. According to local regulations at the time of study conduct.
 
At Screening and Day -1 of each period.
 
At Screening and Day -1 of each period.

MCH= Mean corpuscular hemoglobin; MCV=Mean corpuscular volume, SARS-CoV-2=severe acute respiratory syndrome coronavirus type 2.

Appendix 7 Protocol Amendment History

The information for the current amendment is on the title page.

Protocol Version 2.0 (24 October 2022)

Overall Rationale for the Amendment

This non-substantial amendment was prepared to correct a typographical error in the schedule of activities. The PK sampling at 16 h postdose is not included in the schedule of activities, although the corresponding ECG measurement is included in the schedule of activities. The 16 h postdose blood sampling is present in [Table 1](#) (Time Deviations from PK sampling times, Section [8.4.1](#)) and is also consistently displayed in the ICF.

Additionally, in Section [7.1](#) there was a harmonization with the preexisting next sentence. It was clarified, that if study intervention is permanently discontinued, the participant will remain in the study to be evaluated for safety assessments.

Section # and Name	Description of Change	Brief Rationale
1.3 Schedule of Activities	The PK sampling at 16 h postdose was included.	To correct a typographical error, the PK sampling at 16 h postdose was included.
7.1 Discontinuation of Study Intervention	It was clarified, that if study intervention is permanently discontinued, the participant will remain in the study to be evaluated for safety assessments.	No content change – just harmonization with the preexisting next sentence.

The purpose of this IAP is to document technical and detailed specifications for the final analysis of data collected for protocol MS200527_0070. Results of the analyses described in this IAP will be included in the CSR. Additionally, the planned analyses identified in this IAP may be included in regulatory submissions or future manuscripts. Any post-hoc, or unplanned analyses performed to provide results for inclusion in the CSR but not identified in this prospective IAP will be clearly identified in the CSR.

The IAP is based upon Section 9 (Statistical considerations) of the study protocol and protocol amendments and is prepared in compliance with ICH E9. It describes analyses planned in the protocol and protocol amendments.

The wording used in this IAP is chosen to best match the respective wording in the study protocol template, the CSR template, CDISC requirements and special requirements for table layouts. Therefore, the following approach is used:

Generally, the term 'participant' will be used instead of 'subject' or 'patient'. However, in tables and listings the term 'subject' will be used to match CDISC requirements, except for in-text tables where 'participant' will be used to match the CSR and protocol templates. Similarly, the term 'study intervention' will be used in this document instead of 'treatment' to match protocol and CSR templates, however, tables and listings will use 'treatment' for brevity reasons. Exceptions from this rule are commonly used terms like "on-treatment", "treatment-emergent", "treatment policy", "subject-years", "by-subject", or names of eCRF pages like "Treatment Termination" page.

5 Objectives and Endpoints

| Objectives | Endpoints | Ref. # |
|--|--|--------|
| Primary | | |
| To evaluate whether evobrutinib administered as a single oral dose (as solution) of 45 mg or 225 mg prolongs QT/QTc in comparison to placebo control | ΔΔQTcF (placebo-corrected change from baseline QTcF) for evobrutinib; with concentration-QTc analysis as primary analysis | 1 |
| Secondary | | |
| To demonstrate QTc assay sensitivity | ΔΔQTcF (placebo-corrected change from baseline QTcF) for moxifloxacin | 2 |
| To assess the safety and tolerability of evobrutinib | Nature, occurrence, and severity of TEAEs Absolute values and changes in safety laboratory tests Vital signs assessed from time of first dose to end of study participation Single 12-lead ECGs evaluated by Investigator | 3 |
| To assess the effect of evobrutinib on other ECG parameters | QT, QTcB, QTcl, PR, QRS, RR, HR, cardiologist assessment including T-wave morphology, and U-wave. | 4 |
| To determine the PK of evobrutinib and its major metabolite at 45 mg and 225 mg oral dose (solution) under fasting conditions and moxifloxacin at 400 mg oral dose | AUC ₀₋₂₄ , AUC _{0-∞} , C _{max} , and t _{max} for evobrutinib and major metabolite AUC ₀₋₂₄ , AUC _{0-∞} , C _{max} , and t _{max} for moxifloxacin | 5 |

6 Overview of Planned Analyses

The final, planned analyses identified in the CSP and in this IAP will be performed after the last participant has completed the last visit and after all data queries resolved as well as the database locked.

A data review meeting will be held prior to database lock for the final analysis. In addition, no database can be locked until this IAP has been approved.

7 Changes to the Planned Analyses in the Clinical Study Protocol

Not applicable.

8 Analysis Sets and Subgroups

8.1 Definition of Analysis Sets

| Analysis Set | Description |
|--------------|---|
| SCR | All participants, who provided informed consent, regardless of the participant's enrollment and study intervention status in the study. The analysis of subject disposition will be based on this analysis set. |
| SAF | All participants, who were administered any dose of any study intervention. Analyses will consider participants as treated. All safety analyses and by timepoint and categorical analysis of secondary objectives will be based on this analysis set. |
| PK | The PK Analysis Set is a subset of the SAF, and the PK population will include all participants: Who have completed the study without any relevant protocol deviations and factors likely to affect the comparability of PK results. With adequate study intervention compliance. With evaluable PK data, i.e. nonmissing values for primary endpoints. If participants received prohibited concomitant therapy or medicines, as specified in protocol Section 6.8 they will be excluded from the PK population. All PK analyses will be based on this analysis set. |
| ECG | The ECG Analysis Set will be the basis of the C-QTc analysis and will be a subset of the SAF. Only participants who had a baseline Holter ECG in triplicate and at least one post-baseline Holter ECG in triplicate with a time-matched concentration will be retained for C-QTc analysis. Participants with protocol deviations likely to affect the comparability of ECG measurements or PK concentrations will not be considered in the C-QTc analysis. |

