4.1 Overall Design

Study Design	Single-dose, 4-way crossover
Control Method	Placebo- and positive-controlled
Single or Multicenter	Single center
Study Population Type	Healthy participants
Level and Method of Blinding	Double-blind for evobrutinib and placebo
Bias Minimalization Method(s)	Randomization, blinding
Study Intervention Assignment Method	Randomization
Data and Safety Monitoring /Other Committee:	No
Total Duration of Study Participation per Participant	Up to 57 days, including the Screening Period (maximum of 28 days), 23 days of intervention period with at least a 7-day washout between each study period, and the Safety Follow-up call on Day 29, 1 week after the last dose of study intervention. A study schema and a detailed Schedule of Assessments are provided in Section 1.2 and Section 1.3, respectively.
Provisions for Study Extension or Entry into Roll-Over Studies	Not applicable
Adaptive Aspects of Study Design	Not applicable

A study design schema and a detailed Schedule of Activities are provided in Section 1.2 and Section 1.3, respectively.

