4.2 Scientific Rationale for Study Design

The design of this thorough QT study, a randomized, assessor-blinded, placebo- and positive-(moxifloxacin) controlled, single-dose, 4-period crossover study, is the standard design for this type of QT assessment study.

4.2.1

Use of Moxifloxacin

A positive control is recommended by regulatory authorities to be able to detect a ~ 5 ms change from baseline- and placebo-corrected QTc duration ($\Delta\Delta\text{QTc}$) to confirm the sensitivity of the study. Moxifloxacin is frequently used in thorough QT studies because it induces small and consistent prolongations of QT/QTc but is not considered as having a proarrhythmic activity (as outlined in ICH E14/S7B Q&A 2020). A pooled analysis of 14 crossover thorough QT studies with 400 mg single oral dose of moxifloxacin demonstrated a largest mean $\Delta\Delta\text{QTcF}$ effect of 12.3 ms at 3 h postdose (Yan 2010). In this study, a single 400 mg dose of moxifloxacin will be administered orally to the participants (refer to approved product information).

4.2.2

Participant Input into Design

Not applicable.

4.3

Justification for Dose

Evobrutinib

The evobrutinib therapeutic dose to be used in this study [REDACTED] CCI is expected to result in C_{max} similar to those in the Phase 3 studies in patients dosed with 45 mg tablets (fed) BID, and the supratherapeutic dose [REDACTED] CCI is expected to result in 5-fold higher C_{max} . A [REDACTED] CCI higher C_{max} is expected to provide adequate coverage for the clinically relevant high-exposure scenario for evobrutinib C_{max} , if administered with a moderate or strong CYP3A4 inhibitor [REDACTED] CCI

Moxifloxacin

Moxifloxacin is frequently used in thorough QT studies because it induces a small and consistent QT/QTc prolongation with a low incidence of inducing proarrhythmic activity. A single oral dose of 400 mg given in a fasted state is the standard dose used for this type of study.

4.4

End of Study Definition

The end of the study is defined as the date of last contact (related to this study) with the last participant who participates in this study (last participant's Safety Follow-up Assessment/Early Termination Assessment).

A participant has completed the study if he/she has completed all study parts including the Safety Follow-up Assessment shown in Section 1.3.

Study Termination Criteria

The study will be discontinued or terminated if:

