9.4 Imputation of Missing Data

In this Phase I thorough QT study, missing observations will be assumed to be missing completely at random (MCAR) if not stated otherwise. No action will be taken to handle missing data. A participant who withdraws prior to the last planned observation in a study period will be included in the analyses up to the time of discontinuation.

10 Study Participants

The subsections in this section include specifications for reporting participant disposition and study intervention/study discontinuations. Additionally, procedures for reporting protocol deviations are provided.

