16.1 Pharmacokinetics

PK evaluation will be performed by Nuvisan GmbH.

All statistical analyses and descriptive summaries of PK data will be performed on the PK Analysis Set.

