16.1.2 Descriptive Statistics of PK Parameter Data

PK parameter data of each analyte will be summarized using: number of non-missing observations (n), arithmetic mean (Mean), SD, coefficient of variation (CV%), minimum (Min), median (Median), maximum (Max), geometric mean (GeoMean), the geometric coefficient of variation (GeoCV) and the 95% confidence interval for the GeoMean (LCI 95% GM, UCI 95% GM). For PK parameters related to time (e.g. t_{max} , t_{lag} , t_{last}), only n, Min, Median, and Max may be reported.

Descriptive statistics will only be calculated for a PK parameter when $n > 2$.

PK parameters read directly from the measurements (i.e., C_{max}) will be reported with the same precision as the source data. All other PK parameters will be reported to 3 significant figures. In export datasets, as well as in the SDTM PP domain, PK parameters will be provided with full precision and will not be rounded. Descriptive statistics of PK parameter data will be calculated using full precision values and rounded for reporting purposes only.

The following conventions will be applied when reporting descriptive statistics of PK parameter data:

| | |
|--|----------------------|
| n | 0 decimal place |
| Mean, Min, Median, Max, GeoMean, 95% CI: | 3 significant digits |
| SD: | 4 significant digits |
| CV%, GeoCV%: | 1 decimal place |

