16.1.6 Presentation of PK Concentration and PK Parameter Data

16.1.6.1 Listings and Tables

The following PK tables will be produced (PK Analysis Set):

- Descriptive statistics of concentrations by analyte and study intervention
- Descriptive statistics of PK parameters by analyte and study intervention

The following PK Listings will be produced (Safety Analysis Set):

- Individual concentrations, nominal time by participant, analyte, and study intervention sorted in chronological order
- Individual PK parameters by participant, analyte, and day sorted in chronological order
- PK Sampling date, actual time, nominal time, deviation from time, percentage time deviation by participant, analyte, and study intervention sorted in chronological order
- Phoenix WinNonlin NCA Core Output

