16.1.6.2 Graphical Summaries and Individual plots (PK Analysis Set)

The following graphical summaries and individual plots will be provided:

- Overlaid individual plasma concentration versus time plots on linear and semi-log scale, using actual times, by analyte, and study intervention
- Individual plasma concentration versus time plots overlaid for each study intervention by participant and analyte on linear and semi-log scale using actual times. If any postdose concentration is BLQ the line representing LLOQ will be added to the semi-log plots
- Arithmetic mean concentration time plots; linear (\pm SD for arithmetic mean) and semi-log; using scheduled (nominal) time points by analyte, and study intervention; if any postdose concentration is BLQ the line representing LLOQ will be added to the semi-log plots
- Median concentration time plots; linear and semi-log; using scheduled (nominal) time points by analyte, and study intervention; if any postdose concentration is BLQ the line representing LLOQ will be added to the semi-log plots
- Boxplots for PK parameters $AUC_{0-\infty}$ and C_{max} by analyte, and study intervention

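### The PK analysis set is defined by whole participant (study completers, no prohibited medication), so fully sampled, unaffected PK periods drop out of the PK tables and plots

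*SAP*

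**What the plan says.** SAP Section 8.1 takes into the PK set participants "Who have completed the study without any relevant protocol deviations and factors likely to affect the comparability of PK results", with adequate compliance and evaluable PK data. It then excludes from that set any participant who received therapy prohibited under protocol Section 6.8. Neither condition is limited to a period. Protocol Section 9.3 has the same text.

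Protocol Section 4.4 defines completion: "A participant has completed the study if he/she has completed all study parts including the Safety Follow-up Assessment shown in Section 1.3". Protocol Section 4.1 identifies that assessment as "the Safety Follow-up call on Day 29, 1 week after the last dose of study intervention".

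On use of the set, SAP Section 16.1 states: "All statistical analyses and descriptive summaries of PK data will be performed on the PK Analysis Set". Sections 16.1.6.1 and 16.1.6.2 assign the PK tables and plots to it, while the PK listings use the Safety Analysis Set. The parameter summaries include geometric means and "the 95% confidence interval for the GeoMean" (SAP Section 16.1.2).

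Other sections work on a narrower scale. Under SAP Section 9.4, anyone who "withdraws prior to the last planned observation in a study period will be included in the analyses up to the time of discontinuation". Section 10.2.1 lists concomitant medication among events for the Data Review Meeting and gives flagging of individual values as an example of the action to take. Section 16.1.4 excludes the concentrations and parameters that an important deviation affected. It also keeps a withdrawing participant's data, but only if that participant is still in the PK set.

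**The concern.** Each treatment is a single dose with its own 24-hour sampling, followed by a washout of at least 7 days. A finished period therefore yields a self-contained Cmax and AUC. Whether a participant later withdraws, or takes a supplement in a later washout, does not in itself change a profile already collected. Even so, the set definition removes that profile from the summaries.

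At stake are the geometric means and confidence intervals for evobrutinib 45 mg and 225 mg, the metabolite, and moxifloxacin. They would rest on fewer profiles than the trial collected, for reasons that may have nothing to do with the profiles left out.

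**Working it through.** The visible documents state no dropout rate, medication rate or sample size for this point, so there is no plan figure to reproduce. The check has two parts.

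**1. Reading the rules together**

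- *Completion.* With 7-day washouts the last PK sample falls on Day 23 (24 h after the Day 22 dose, protocol Section 1.3). The call that completes the study is on Day 29, after all sampling.
- *Withdrawal.* SAP Section 9.4 would keep data up to discontinuation. Section 16.1.4 makes this depend on PK set membership, which a participant who withdraws from the study does not have under Section 8.1. The retention sentence in 16.1.4 is left with almost nothing to act on.
- *Medication.* Protocol Section 6.8.3 counts vitamins and antacids as prohibited. One such item in the washout before period 4 removes periods 1 to 3 as well under SAP Section 8.1. Under Sections 10.2.1 and 16.1.4 alone, only affected values would go.

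**2. Size (all rates are assumptions)**

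Input from the documents: four sequences, with each treatment once in each period position (protocol Section 6.3.1). Assumed: dropout share d = 0.05, 0.10, 0.15; k complete periods per dropout; every finished period of a dropout is valid.

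Share of complete periods discarded = k·d / [4(1 − d) + k·d].

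| Dropout pattern | d = 5% | d = 10% | d = 15% |
|---|---|---|---|
| All after period 1 (k = 1) | 0.05/3.85 = 1.3% | 0.10/3.70 = 2.7% | 0.15/3.55 = 4.2% |
| Even over periods 1–3 (mean k = 2) | 0.10/3.90 = 2.6% | 0.20/3.80 = 5.3% | 0.30/3.70 = 8.1% |
| All after period 3 (k = 3) | 0.15/3.95 = 3.8% | 0.30/3.90 = 7.7% | 0.45/3.85 = 11.7% |

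With even spread, each treatment has been given to half of the dropouts. The number per treatment, as a share of N, is 1 − d as written and 1 − d/2 by period: 95/90/85% against 97.5/95/92.5%. The ratio of standard errors of a log-scale mean is √[(1 − d/2)/(1 − d)] = 1.013, 1.027, 1.043.

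Example with an assumed N = 32 and d = 10%: 28.8 per treatment as written against 30.4 by period. Dropouts hold on average 1.5 complete active periods, so 3.2 × 1.5 = 4.8 are lost. As a share of complete active periods this is 4.8/(3 × 28.8 + 4.8) = 4.8/91.2 = 5.3%, which agrees with the table.

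*Missed call (hypothetical).* If a further 2% of the remaining participants missed only the Day 29 call, the even-spread share becomes [2d + 4(1 − d)(0.02)] / [4(1 − d) + 2d] = 0.176/3.90, 0.272/3.80, 0.368/3.70 = 4.5, 7.2, 9.9%.

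*Prohibited medication.* If a share m of participants is affected, in a of 4 periods each, the participant rule removes m of all periods and a period rule removes m·a/4. For m = 2, 5, 10%, the period rule removes 0.5, 1.25, 2.5% (a = 1) or 1, 2.5, 5% (a = 2).

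**The case against.** The strongest defence is that the definition is a deliberate choice. Its stated aim is comparability of PK results, and in a crossover a completer set keeps the 45 mg, 225 mg and moxifloxacin summaries on the same people. A fixed medication rule also needs no judgement. The trigger is narrower than it first looks, because protocol Section 6.8 permits paracetamol and case-by-case exceptions. Some reasons for stopping in protocol Section 7.1, such as significant noncompliance or unmet eligibility criteria, may themselves justify exclusion, so not every period counted above is sound.

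These points stand, and they keep the finding small. They do not remove it: the PK summaries are by treatment and purely descriptive, so identical participants across treatments are convenient but not required.

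The defence also says that the sections do not contradict each other. This is largely fair. SAP Section 9.4 is a missing-data rule, 10.2.1 gives value flagging only as an example, 10.2.2 provides for both levels of exclusion, and 16.1.4 lets set membership govern. That order of precedence confirms the loss of data, however; it does not cure it.

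A reader might take the denominator sentence in SAP Section 9 as evidence that a completer set was not intended. It does not show this: it governs proportions for safety, QTc and PK summaries together, and a completer set satisfies it too.

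**Conclusion.** The point holds as a modest, inexpensive improvement to the secondary descriptive PK. Taken literally, the plan leaves complete and unaffected profiles out of every PK table and plot. With even dropout of 5 to 15% and all finished periods of dropouts taken as valid, the standard error of a log-scale mean rises by 1.3 to 4.3%. The rates are assumptions, and the missed-call case is hypothetical.

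Two stronger readings are not supported:

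- *That the primary analysis is affected.* The concentration-QTc analysis uses the ECG set, which has no completion condition. Assay sensitivity is read at the geometric mean moxifloxacin Cmax, but the visible text does not say which set supplies that value and SAP Section 16.3.4.1 is partly redacted. No error can be claimed there.
- *That the summaries are biased.* Adverse events are one reason for withdrawal, so selection of completers is possible, but nothing in the documents shows it.

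**What to change.** In SAP Section 8.1, for the PK set only and before database lock:

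1. Replace the study-completion condition with inclusion of each treated participant's periods that have an evaluable PK profile and no PK-relevant deviation in that period.
2. Limit the prohibited-medication exclusion to the affected period or periods, decided at the Data Review Meeting before database lock.
3. As an editorial change, replace the reference to primary endpoints with the objective 5 PK parameters. The study's primary endpoint is ΔΔQTcF, although the intended meaning can be recovered from SAP Sections 5 and 16.1.3.
4. Record the change in SAP Section 7, which now says not applicable, because protocol Section 9.3 carries the same definition.

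The ECG set needs no change on this account.

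Cost: a few sentences and no new data. Numbers per treatment may differ, so the 45 mg, 225 mg and moxifloxacin summaries may not rest on the same participants; the tables already report n. The medication decision becomes a documented judgement in place of a fixed rule.
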